Across both sites, we anticipate recruiting, consenting, and screening approximately 240 male and female Veteran and active duty military subjects (~120/site), between the ages of 18-70 years, in order to meet the target enrollment goals. In order to account for subject drop outs and the potential need to discontinue subjects before study completion (see below for discontinuation criteria) and retain a sample of ~159 subjects completing the double-blind treatment phase (~53 per treatment group), approximately 198 eligible subjects (~66 in each group) who meet criteria for PTSD as determined by the Clinician Administered PTSD Scale (CAPS-5) and the study inclusion criteria outlined below, will be randomized.

At the West Haven VA, we intend to randomize approximately 99 Veteran and active duty military personnel. In order to account for subject dropouts and the potential need to discontinue subjects before study completion (see below for discontinuation criteria) and retain a sample of at least ~80 subjects completing the double-blind treatment phase, approximately 120 eligible subjects (see below for eligibility criteria), will be randomized into the study.

B. Inclusion and Exclusion Criteria:

Inclusion Criteria:

1. Male or female Veterans and active duty military personnel between the ages of 18-75 years seeking treatment for PTSD.
2. Diagnosis of PTSD with a score of 23 or higher (i.e. severe PTSD) on the Clinician-Administered PTSD Scale (CAPS-5) at screening.

3. Treatment resistance to at least one adequate trial of an antidepressant as determined by the Massachusetts General Hospital Antidepressant Treatment History Questionnaire (MGH-ATRQ).
4. Subjects on prescribed nicotine replacement therapy (i.e. patch/lozenge) may enter the study and continue the prescribed nicotine treatment for the duration of their participation. Should the participant plan to use their nicotine replacement therapy during infusion visits, it is asked that they bring in the original packaging with the prescription label on it.
5. Subjects on FDA-approved antidepressant, trazodone, atypical neuroleptic, prazosin, or clonidine may enter the study if they have been on an overall stable treatment, as determined by the study clinician, for at least 4 weeks prior to randomization. Following randomization, changes to doses may be allowable at the investigator's discretion.

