Sample size justification: Murrough et al. reported large effect sizes (all d 's > 1.42) in a study of open-label repeated doses of ketamine for depression.²¹ In the recent study of a single infusion of ketamine in PTSD,²⁷ there was a medium effect size (Cohen's $d=0.6$) for the comparison between change in PTSD symptoms on ketamine and midazolam from baseline to 24 hours post-infusion. In our study, we expect that the effect size for the comparison between the higher dose ketamine vs. lower dose ketamine will be similar (i.e. Cohen's $d=0.6$). Furthermore, the effect size for the comparison between the higher dose ketamine and placebo is expected to be much larger (effect size of at least $d=0.8$) since response on placebo will be smaller than response on an active comparator and our trial has significantly longer duration than the Feder et al. study. This effect size is still much smaller than the estimated effect sizes for the corresponding comparison in subjects with major depression observed by Murrough et al.²¹ Based on the effect sizes for the individual comparisons, the expected effect size for the overall treatment by time interaction is medium (Cohen's $f=0.24$). Thus we estimate that we need 53 subjects per group to test the

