primary hypotheses with at least 80% power at two-sided alpha level of 0.05. In particular, with 53 subjects per group we have 87% power to detect a treatment by time interaction of magnitude $f=0.24$ and 80% power to detect pairwise differences of magnitude $d=0.6$ or higher at two-sided alpha level of 0.05. Holm-Bonferroni adjustment will be used for the pairwise comparisons and is taken into account in the power calculation so that the family-wise error rate for the pairwise comparisons is kept at 0.05 level. Testing of between group differences over time will be performed within the mixed effects models which are expected to be even more powerful since they use all available data on each individual including data on subjects who dropout or have intermittent missing data due to non-compliance with the treatment schedule. To address potential limitations related to the external validity, we have expanded the age range (18-70), included active duty military personnel and non-OEF/OIF/OND Veterans, and will use stratified randomization to match and balance on study site and alcohol use comorbidity during the trial. Additionally, we plan to track participant duty status, years since trauma and treatment history, and examine these factors in post-hoc analyses.

Analysis plan: Descriptive statistics will be calculated prior to statistical analysis. Distributions of quantitative variables will be assessed for normality using normal probability plots and Kolmogorov-Smirnov statistics and transformations or non-parametric methods will be used as necessary. All statistical tests will be two-sided. Uncorrected alpha level of 0.05 will be used for testing the primary hypothesis as described below. Pairwise post-hoc comparisons and tests of secondary outcome measures will be adjusted using Holm-Bonferroni procedure. Randomized treatment groups will be compared at baseline on potentially confounding factors (e.g. age, sex, history of substance abuse) and variables that are significantly different between groups will be included as additional covariates in the models below. All analyses will be intent-to-treat.

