status, substance abuse, age, and gender by adding these factors one at a time to the models above and testing interactions between each potential moderator and treatment group. We will follow the approach of Kraemer et al. (2002) for testing moderator effects. A secondary analysis of PTSD remission rates (patients in each group who attain a total CAPS-5 score < 23 at the end of the double-blind treatment; i.e. mild/subthreshold PTSD according to CAPS-5 criteria) will be done using two-tailed χ^2 tests in logistic regression analyses that control for site and alcohol abuse comorbidity effects. Dropout rates will be compared across groups and sensitivity analyses using pattern-mixture models will be performed if there are disproportionate dropout rates in the treatment arms of this trial or concerns that the data are not missing at random. Effects of intermittent missing data due to non-compliance with treatment schedule can also be assessed using these models.

Primary efficacy measure justification: After considering alternative measures, we have selected the PCL-5 as the primary outcome measure of this study.²⁸⁻³² The PCL is a well validated PTSD scale with good internal consistency,²⁹ and test-retest reliability.^{31,63} While the Clinician Administered PTSD Scale (CAPS) is widely recognized as the gold standard measure to assess efficacy and symptom remission in clinical trials of PTSD, the CAPS is not designed for use in short repeat intervals, such as those incorporated in the present trial (i.e. 24-hours post-infusion) and it would be burdensome for subjects to complete this assessment multiple times over the course of the study, which may also compromise the validity of reports. Additionally, other commonly used short clinician administered instruments, do not accommodate the assessment intervals of the study, may not capture rapid changes associated with medication treatment and some symptoms would produce null results within short time intervals. As a quality control measure for use of the patient rated PCL-5 as a primary outcome instrument, we will repeat the CAPS-5 assessments at the end of treatment and the end of follow-up, and compare these findings to the patient based ratings. Strong correlations have been previously reported between the PCL and the CAPS during validation of the psychometrics for this instrument.^{31,32,34}

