## Supplemental

Mixed models were constructed to evaluate the effects of posttraumatic stress disorder (PTSD) treatment on the PTSD Checklist for DSM-5 (PCL-5), Clinician-Administered PTSD Scale for DSM-5, Montgomery-Asberg Depression Rating Scale (MADRS), Clinician-Administered Dissociative State Scale (CADSS), and Positive and Negative Syndrome Scale (PANSS) based on all available observations within individual patients. Treatment group (Standard, Low, Placebo), time (pre each infusion, 24 hours post-first and post-last infusions for PCL-5 and MADRS, baseline and post-last infusion for CAPS-5, during each session for CADSS and PANSS), site and all possible interactions were fit as fixed effects. Alcohol use disorder (AUD) diagnosis was included as a covariate. The CADSS and PANSS models also included interval (30 and 120 minutes) and the interaction between interval and treatment. Subject was the clustering factor. The best-fitting variance-covariance structure in each model was selected based on Bayesian information criterion. Residuals were assessed, and CADSS was logtransformed to correct for positive skewness of this outcome. In the final models, nonsignificant interactions not involving treatment were dropped for parsimony. Focused least square mean comparisons of change from baseline to 24 hours post-first infusion and from baseline to 24 hours post-last infusion within treatment group, and for pairwise differences in change from baseline between treatment groups, were evaluated regardless of the significance of the interactions and main effects. Follow-up data on the PCL-5 and CAPS-5 also were analyzed using mixed models covarying for baseline severity. Individuals with open label treatment were excluded from these analyses. Responder status was calculated as at least 25% improvement from pretreatment on the PCL-5. Missing data were treated as failure (i.e., nonresponder). The primary analyses for the binary outcomes were logistic regressions with treatment, site, and AUD as predictors, and missing treated as failure. The treatment by site interactions were nonsignificant and were dropped for parsimony in the final models.

For the PCL-5 self-assessments, 1.6% of assessments specified incorrect index trauma event referenced for symptom scoring, and 23.6% of assessments were completed without specifying the index trauma. A sensitivity analysis determined that mixed methods ANOVA results were essentially unchanged with or without their inclusion.

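### The CAPS-5 remission model would usually leave out baseline CAPS-5, at a nil-to-modest cost in power on one secondary endpoint

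*Protocol*

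**What the plan says.** The Protocol's Analysis plan (section IV.F) defines PTSD remission by the number of "patients in each group who attain a total CAPS-5 score < 23 at the end of the double-blind treatment". The groups are compared by two-tailed chi-square tests in "logistic regression analyses that control for site and alcohol abuse comorbidity effects". Baseline CAPS-5 is not in that model.

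One general rule could bring it in. The Analysis plan compares the arms at baseline, and "variables that are significantly different between groups will be included as additional covariates in the models below". So the covariate depends on a significance test, not on how well it predicts the outcome.

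The SAP (Supplemental) gives one model for binary outcomes: "logistic regressions with treatment, site, and AUD as predictors, and missing treated as failure". It does not name remission; the only binary outcome it defines is PCL-5 response. The SAP does covary for pretreatment severity in the follow-up mixed models, so the device is already in use elsewhere in the plan.

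Table 2 schedules CAPS-5 at screening (Visit 1) and after the last double-blind infusion (Visit 11). Inclusion criterion 2 requires a screening score of at least 23.

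**The concern.** Where a patient starts on CAPS-5 is likely to influence whether that patient ends below a fixed line on the same scale. If it does, a logistic model without the screening score leaves explainable variation in the residual and tests treatment less efficiently than it could. Site and alcohol comorbidity do not replace the score, and the significance-triggered rule would rarely admit it.

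What is at stake is power for one secondary endpoint. That endpoint may also face a stricter threshold than 0.05, because "Pairwise post-hoc comparisons and tests of secondary outcome measures will be adjusted using Holm-Bonferroni procedure".

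**Working it through.** **1. The plan's own power figure.** No power is stated for remission. The nearest figure is 80% for a pairwise difference of d = 0.6 with 53 per group (Sample size justification).

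- Power = Φ(d√(n/2) − z), with 0.6 × √26.5 = 3.089.
- At α = 0.05/2, z = 2.241 and power is Φ(0.848) = 80.2%. The stated figure reproduces here.
- At α = 0.05 power is 87.0%; at 0.05/3 it is 75.6%.

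This figure concerns the primary hypotheses, so it sets no target that the remission analysis misses.

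**2. How often the covariate rule acts.** Under randomisation, a baseline test at 0.05 is significant in 5% of trials by construction. Modelled as a three-arm ANOVA of baseline CAPS-5, the rule added the covariate in 4.7–5.8% of simulated trials. Its largest gain in power was 0.9 points (75.1% to 76.0%).

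**3. Simulation inputs.**

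*From the Protocol:*
- 66 randomised per arm and about 53 completing; 53/66 = 0.80, so 20% missing.
- d = 0.8 for 0.5 mg/kg against placebo and 0.6 between doses, so 0.8 − 0.6 = 0.2 for 0.2 mg/kg against placebo. On the first of these the protocol says "the effect size for the comparison between the higher dose ketamine and placebo is expected to be much larger".
- Entry at 23 or higher; remission below 23.

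*Assumed:*
- Baseline mean (SD) of 32 (8), 38 (9) or 44 (9), rounded and truncated to 23–80.
- End-score SD 12; mean fall of 10 on placebo.
- Half of patients at each site; 30% with alcohol use disorder.
- Missing completely at random and coded as failure, that is, the SAP's rule taken to cover remission.

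End score = mean baseline − 10 − 12 × effect + 12 × (r·z + √(1 − r²)·noise), where z is the standardised baseline and r the baseline-to-end correlation. The shifts are 12 × 0.8 = 9.6 and 12 × 0.2 = 2.4 points. The logistic model has treatment, site and alcohol use disorder, fitted without and with baseline CAPS-5. The test is the Wald contrast of 0.5 mg/kg against placebo, in 1,500 to 5,000 trials per setting, repeated with different seeds.

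**4. Results at two-sided 0.05.** For r from 0.3 to 0.7, power without baseline CAPS-5 is about 75–85%, depending on the assumed baseline.

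| Correlation r | Gain in power from adding baseline CAPS-5 |
|---|---|
| 0 | about nil (within 0.7 points) |
| 0.3 | 1–2 points |
| 0.5 | about 4 points |
| 0.7 | 7–10 points |

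With no treatment effect, the rejection rate is 4.0–5.1% without and 4.2–5.5% with the covariate. Both models are valid.

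**5. Does the shared cut-off matter?** Entry was kept at 23 and the remission line moved (baseline 38 (9), r = 0.5).

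| Remission below | Power without | Power with | Gain |
|---|---|---|---|
| 20 | 83.9% | 87.9% | 4.0 |
| 23 | 85.5% | 88.6% | 3.1 |
| 26 | 82.2% | 86.3% | 4.1 |

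The gain is 3 to 4 points wherever the line falls.

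**6. Sensitivity.**
- *Overall 2-df treatment test:* gains are similar, about 1–3 points at r = 0.3, about 4 at 0.5 and 9–12 at 0.7.
- *α = 0.05/3* (strictest Holm step if the family is three pairwise comparisons): power without the covariate is about 59–71%; gains are about 2, 4–6 and 11–12 points.
- *Smaller effect, 0.6 SD* (baseline mean 40 or 33, end-score SD 11, same 66 per arm and 20% missing): at r = 0.5, 60.0% to 66.1% and 57.9% to 62.7%; at r = 0.7, 60.1% to 71.8% and 55.0% to 66.1%; at r = 0, no gain.

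**The case against.** Adjusting for the two stratification factors is a legitimate prespecified model. Its type I error is sound, no power was promised for remission, and the size of improvement is analysed separately through the continuous CAPS-5 and PCL-5 models. The gain rests on inputs that the documents do not give: it vanishes at correlation 0, and both the starting power and the gain move with the assumed effect and SD. The SAP does not name remission, so carrying its missing-as-failure rule over is an assumption. The SAP is written in the past tense, so prespecification may no longer be possible. All of this stands, and it keeps the point minor. A further objection, that the planned test may be the 2-df treatment test and not a pairwise contrast, does not change the result, because the gains are similar.

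Three stronger readings are tempting, and the documents support none of them.

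- *The coincidence of the entry and remission cut-offs causes the loss.* A patient entering at 23 needs a 1-point fall and one entering at 40 needs 18, so a reader might infer this. Step 5 shows the same gain with the line at 20 or 26. The loss comes from omitting a prognostic score.
- *The comparison is biased or confounded.* Randomisation protects it, and the null rejection rates show no inflation.
- *The severity labels are an error.* The protocol calls scores of 23 or more severe and scores below 23 mild/subthreshold. The two ranges meet without gap or overlap, and no analysis uses the words.

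**Conclusion.** The point holds as a minor matter of efficiency. As written, the remission analysis would leave out baseline CAPS-5 in about 95% of trials (100% − 5%), although the score is already collected.

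Under the stated assumptions (d = 0.8 carried over to the CAPS-5 end score, 66 per arm, 20% missing as failure, pairwise test at two-sided 0.05), the cost runs from nothing at correlation 0 to 7–10 points of power at 0.7. The true correlation is unknown from the documents, so no single figure in that range can be claimed. The primary PCL-5 analysis, the continuous CAPS-5 mixed model and the validity of the remission comparison are unaffected.

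**What to change.** Include screening CAPS-5 total as a continuous covariate in the remission logistic model, beside treatment, site and alcohol comorbidity, whether or not the arms differ on it. Report a standardised risk difference with its confidence interval beside the odds ratio. Leave the remission definition unchanged.

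If the analysis has already been run, show the adjusted model beside the original and label it post hoc.

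The cost is one covariate in one model and no new data. The downside is that the odds ratio becomes conditional on baseline severity and so is not directly comparable with the unadjusted one; the standardised risk difference keeps a marginal summary available.
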